8.2 Laboratory Evaluations

8.2.1 Clinical Laboratory Evaluations

Approximately three mls of blood will be obtained at admission, and a fingerpick blood sample will be taken every 6 hours for the next 48 hours. Fingerpick samples will be approximately 200 μl in volume, resulting in an approximate total blood volume obtained of 3.6 mls.

An evaluation of malaria parasitemia (MP) and hematocrit (packed cell volume (PCV)) will be performed at initial screening and every six hours thereafter. These exams will continue until two consecutive examinations show an absence of malaria parasites. MP evaluation is performed on a thick blood smear. PCV is determined in a microhematocrit tube.

Lumbar puncture: A lumbar puncture will be attempted at the time of admission on all children admitted to the PRW, and if successful, the opening pressure (mm CSF) will be recorded. This is performed to eliminate meningitis as an alternate etiology of coma. Cerebral spinal fluid (CSF) will be sent for cell count, differential, and culture. 1 ml of the total 4 ml volume will be archived for subsequent studies of biomarkers of increased brain volume.

Respiratory swab: All participants will have a nasopharyngeal swab collected at the time of admission. These will be batch analyzed (after hospitalization) to detect respiratory viral pathogens.

Red Blood Cell (RBC) Cryopreservation: RBCs will be cryopreserved and sent to an outside institution for bio-banking/future analysis.

Blood for culture will be obtained on all participants admitted to the PRW. Blood will be obtained from either a peripheral or femoral vein and transferred to a pediatric BacTec bottle for subsequent analysis.

Plasma for archive: One ml of blood will be collected in a lithium heparin anticoagulated tube. Plasma will be separated and archived for subsequent studies of biomarkers of increased brain volume.

Urine for archive: Urine will be collected either while inserting an indwelling urinary catheter *or* by attaching a sterile urine collection bag to the perineum, and at least one ml will be archived for subsequent studies of biomarkers of increased brain volume.

Blood glucose levels will be measured using point of care testing on admission and every 6 hours thereafter until the participant has maintained a BCS of 3 for greater than 4 hours. Machines will be checked for accuracy each morning with a manufacturer supplied test strip.

Lactate levels will be determined on admission and every six hours thereafter until the participant has maintained a BCS of 3 for greater than 4 hours. Testing is done with a point of care testing machine. This test uses one drop of blood obtained by finger prick. The monitor will be tested for accuracy on manufacturer supplied test strips every morning.

HIV testing will be performed on all participants, subject to permission being granted by the parent/ guardian present. The test will be performed after recovery of the participant is anticipated by the clinical staff unless test results are thought to have relevance for acute clinical care. Two rapid tests will be performed on a blood sample obtained by finger prick. In the event of discordant results an HIV polymerase chain reaction test will be performed.

Full Blood Count: Participants will have blood drawn for a full blood count (FBC) on admission. FBC includes hemoglobin, hematocrit, RBC indices, white blood cell (WBC) with 5-part differential, and platelet count.

Electrolytes: Participants enrolled in the study who are randomized to hypertonic saline administration will have electrolytes evaluated on admission and every six hours thereafter until they regain consciousness. As this is a crucial measurement in the appropriate administration of the investigational product, a back-up machine will be available.

Respiratory infection screening: On admission, two nasopharyngeal swabs: one for viral identification and one for bacterial detection and quantification by real time PCR. For viral identification we will use the respiratory PCR panel (FilmArray) which includes simultaneous detection of 18 viruses (adenovirus, 4 endemic coronaviruses, SARS-CoV-2, hmpv, RSV, 5 influenza viruses, rhinovirus/enterovirus and 4 parainfluenza viruses). Individual bacterial real time PCR analysis and quantitation will be performed for *Staphylococcus aureus*, *Streptococcus pneumoniae*, *Haemophilus influenzae*, and *Moraxella catarrhalis*.

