 - Continuous monitoring of heart rate and rhythm from EKG, respiratory rate, and pulse oximetry via monitor, and blood pressure via arterial line or cuff. Signals will be archived for offline analyses aimed at identifying heart rate variability patterns over time associated with CM and with clinical improvement or decline in association with treatment.

- Electrolytes and acid-base balance 3-hourly during the first 24 hours and 6-hourly thereafter (in those randomized to hypertonic saline)
- PRW and PICU
 - 2-hourly assessments of vital signs (including temperature) and Blantyre Coma Score until BCS = 5 and temperature is $\leq 37.5^{\circ}\text{C}$ for 24 hours, then 6-hourly.
 - 6-hourly assessments of malaria parasitemia and hematocrit, until two consecutive parasitemia counts are negative.
 - 12-hourly neurological examinations,
 - Daily ophthalmoscopy while unconscious
 - Daily ONSD measurements (while unconscious)
 - Daily TCD examinations
 - Daily MRI examinations (while unconscious if participant is clinically stable for transportation to undergo neuroimaging)

The primary objective (treatment success or failure) will be determined within the first 7 days of hospitalization (Figure 8)

Secondary objectives (Figure 8)

1. The secondary objective involving neurological sequelae at 1, 6, and 12 months after randomization will be determined in survivors randomized in the clinical trial.
2. The secondary objective of identifying surrogate measures of increased brain volume will include participants in the clinical trial as well as study subjects who are screened but do not meet inclusion criteria for clinical trial enrollment e.g. their brain volume is not increased enough to qualify for enrollment in the trial and are therefore not randomized.
3. The secondary objective of assessing the safety of early intubation and mechanical ventilation will include participants in the clinical trial as well as study subjects with CM who are screened but do not meet inclusion criteria for clinical trial enrollment e.g. their brain volume is not increased enough to qualify for enrollment in the trial and are therefore not randomized.
4. TCD endpoints will be determined on all participants (see section 7.2.2.4)]

Choice of participant population and sample size considerations

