1. Arm 1: Usual care + immediate mechanical ventilatory support (VENT) for a maximum of 7 days, with ventilator withdrawal once brain volume has decreased (brain volume score ≤ 5) or the patient has improved clinically (modified Blantyre Coma Score ≥ 3) or the patient dies or meets criteria for severe irreversible neurologic failure.
2. Arm 2: Usual care + intravenous hypertonic saline (HPS) for a maximum of 7 days, withdrawn once brain volume has decreased (brain volume score ≤ 5) and the patient

has improved clinically (Blantyre Coma Score ≥ 3) or the patient dies or meets criteria for severe irreversible neurologic failure.

3. Arm 3: Usual care (UC); intravenous fluids, intravenous artesunate; antipyretics, anticonvulsants and blood transfusions as needed; nutritional support) for a maximum of 7 days, or until brain volume has decreased (brain volume score ≤ 5) and the patient has improved clinically (Blantyre Coma Score ≥ 3) or the patient dies or meets criteria for severe irreversible neurologic failures

Participants will remain in the study throughout their hospitalization and, in survivors, through the 12-month post-randomization follow-up visit. Children are discharged when two sequential 6-hourly blood films are free of malaria parasites, when they have been afebrile for 24 consecutive hours, and when they are able to take medications and food by mouth. Final data collection will be at 12 months post-randomization.

Stratification:

No stratification is required. The ages of retinopathy-positive CM with severely increased brain volume per MRI who survived were compared to those of participants from the same population that died. There was no difference in the age structure (data not shown, $p=0.95$).

Primary and secondary outcomes.

The primary outcome is treatment success or failure, determined within the first 7 days. Treatment success is recovery. Treatment failure is death, ventilatory rescue (for participants in Arms 2 and 3) or meeting criteria for severe irreversible neurologic failure.

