- Arm 1: Usual care + immediate ventilatory support for a maximum of 7 days. These subjects will undergo rapid sequence intubation and be placed on a mechanical ventilator to maintain physiological pCO_2 levels for a maximum of 7 days. Arterial blood gas determinations will take place every 3 hours for the first 24 hours, then every 6 hours until the participant is extubated. Non-scheduled blood gas determinations may occur at the discretion of the PICU physician. Participants will remain in the Pediatric ICU during mechanical ventilation and after its discontinuance.
- Arm 2: Usual care + infusion of 3% hypertonic saline to achieve a target blood concentration of 150-160 mmol/L. Participants will remain in the Pediatric ICU during hypertonic saline infusion. Participants randomized to hypertonic saline administration will have electrolytes evaluated on admission and every six hours thereafter until they regain consciousness ($\text{BCS} \geq 3$)
- Arm 3: Usual care (elevation of the head of the bed 30 degrees and intravenous antimalarial drugs).

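### Section 8.2.1's blood total of 3.6 mL does not follow from its own inputs, which give 4.6 mL, and Appendix A's film schedule conflicts with the text from Day 2

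*Combined protocol and SAP*

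**What the plan says.** **Blood volume.** The opening paragraph of Section 8.2.1 gives all the inputs and a total:
- The draw on arrival is put at about 3 mL.
- The frequency of later sampling is given as "a fingerpick blood sample will be taken every 6 hours for the next 48 hours".
- Each of those later samples is put at about 0.2 mL.
- The sum is then printed, "resulting in an approximate total blood volume obtained of 3.6 mls".

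**Film and PCV schedule in the text.** The next paragraph of Section 8.2.1 starts malaria films and PCV at screening, repeats them 6-hourly, and sets the stopping rule: "These exams will continue until two consecutive examinations show an absence of malaria parasites". Section 8.1 has the same rule and adds that both tests use fingerprick blood. Section 4 agrees: "6-hourly assessments of malaria parasitemia and hematocrit, until two consecutive parasitemia counts are negative". None of these places sets a time limit or mentions the child's level of consciousness.

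**Film and PCV schedule in Appendix A.** The Schedule of Events has an admission entry and four unbracketed entries on Day 1. The entries for Day 2 and for Days 3-7 are all bracketed. The key defines a bracket as applying only to a child who has not regained consciousness.

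**Discharge.** Section 4 states: "Children are discharged when two sequential 6-hourly blood films are free of malaria parasites". Being afebrile and able to take food and medication by mouth are further conditions.

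**The concern.** The volume sentence carries its own inputs, and they do not add up to the printed figure. It is the only total blood volume in the protocol text supplied. The children may be as young as 6 months (Section 5.1), and the two groups compared in Section 4 had mean hematocrits of 23.36% and 25.54%. A sampling-burden figure for such children should be correct and should say what it covers.

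The second problem is operational. Ward staff are likely to work from the Schedule of Events. If they did, they would stop films at the return of consciousness from Day 2 onward, while the body text would have them continue until parasite clearance. The discharge rule relies on those later films in any child who has not already cleared. Hematocrit follow-up after waking would also depend on which part of the protocol was followed.

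**Working it through.** **1. Try to reproduce 3.6 mL.** Inputs from Section 8.2.1: admission draw 3.0 mL, fingerprick 0.2 mL, interval 6 h, window 48 h.

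Total = admission volume + (number of fingerpricks × 0.2 mL).

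| Way of counting | Fingerpricks | Total (mL) |
|---|---|---|
| 48/6, after admission | 8 | 3.0 + 1.6 = 4.6 |
| Also counting one at time 0 | 9 | 3.0 + 1.8 = 4.8 |
| Dropping the one at 48 h | 7 | 3.0 + 1.4 = 4.4 |
| Fingerpricks alone | 8 | 1.6 |

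None gives 3.6 mL. The gap is 4.6 − 3.6 = 1.0 mL. Then 1.0/3.6 = 28% above the printed figure; equivalently, the printed figure is 1.0/4.6 = 22% too low.

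**2. What would give 3.6 mL?**
- Number of fingerpricks: (3.6 − 3.0)/0.2 = 3, which covers 18 h.
- Admission draw, keeping eight fingerpricks: 3.6 − 1.6 = 2.0 mL.
- Fingerprick volume, keeping eight and 3.0 mL: 0.6/8 = 0.075 mL.

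Any one of these changes restores the sum. The documents support none over the others.

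**3. Totals under the other two descriptions,** at the same 3.0 mL and 0.2 mL:
- *Until clearance (Sections 4, 8.1, 8.2.1).* There is no fixed total. Children are parasitemic at entry, so the earliest two negatives are the 6 h and 12 h films: 3.0 + 2 × 0.2 = 3.4 mL. Negatives at 12 h and 18 h give 3.6 mL, and eight samples give 4.6 mL. Each further day adds 4 × 0.2 = 0.8 mL.
- *Appendix A.* Conscious from Day 2: 3.0 + 4 × 0.2 = 3.8 mL. Unconscious through Day 2: 3.0 + 8 × 0.2 = 4.6 mL. Unconscious through Day 7, reading the Days 3-7 column as four samples daily: 3.0 + 28 × 0.2 = 8.6 mL.

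**4. Follow one child through the two film schedules.** Take a child who is conscious from Day 2 and has not yet had two negative films in a row.
- Sections 4, 8.1 and 8.2.1: films continue 6-hourly.
- Appendix A: every remaining inpatient film entry is bracketed, so none is scheduled.
- Section 4 discharge rule: two sequential negative 6-hourly films are still needed.

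A child who already has two negatives from the unconditional Day 1 films meets no conflict.

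**5. Samples outside the printed total.** The sentence covers the admission draw and fingerpricks only.
- *VENT.* Section 8.1 states: "Arterial blood gas determinations will take place every 3 hours for the first 24 hours, then every 6 hours until the participant is extubated". Over the 7-day maximum that is 24/3 + 144/6 = 8 + 24 = 32 samples. No volume per sample is stated.
- *HPS.* Electrolyte frequency differs by section. Over 48 h after baseline, Section 4 (3-hourly for 24 h, then 6-hourly) gives 8 + 4 = 12. Section 6.3 (3-hourly for 12 h, then 6-hourly) gives 4 + 6 = 10. Sections 8.1 and 8.2.1 (6-hourly throughout) give 8. No HPS total can be fixed until these agree.

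**The case against.** The strongest reply is that this is a 1 mL slip in a figure labelled approximate, together with a mismatch in a summary grid whose body text is clear. Three places in the text agree on the film rule and match the discharge rule. The grid's film row has the same inpatient pattern as the lactate and glucose row, where the text does intend stopping on coma recovery, so the brackets may simply have been carried across. This stands as a limit on importance. It does not remove the error: no way of counting the stated inputs gives 3.6 mL, and the grid still contradicts the text.

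A reader might infer more than the documents support:
- *That 3.6 mL is wrong under every schedule.* It is tied only to the 48 h sentence. The until-clearance rule has no fixed total, and a child who needs exactly three fingerpricks totals 3.6 mL.
- *That discharge cannot be assessed in awake children.* The Day 1 films are unconditional, so the gap is confined to children conscious from Day 2 without two earlier negatives, and the text does require films for them.
- *That there are three competing film schedules.* The 48 h sentence does not name films or PCV. The link is an inference from Section 8.1, which says they are taken by fingerprick. The explicit conflict is between the text and Appendix A.
- *That 4.6 mL is certainly the intended figure.* A 2 mL admission draw would make the printed total right.
- *That VENT children lose a further 3 to 16 mL.* That takes 32 gas samples at an assumed 0.1 to 0.5 mL each. It needs a full 7 days of ventilation, and Section 6.7 leaves the arterial line for gases to the intensivist's discretion.
- *That totals near 8.6 mL are typical.* Section 2.3 says that nearly all survivors are discharged within 72 hours of admission.

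**Conclusion.** The concern holds in two limited parts. First, the 48 h inputs in Section 8.2.1 sum to 4.6 mL (4.4 to 4.8 mL), not 3.6 mL. This takes the 3 mL draw, 0.2 mL fingerprick and 6-hourly interval as printed; whether an input or the total is the slip is unknown. Second, Appendix A conflicts with Sections 4, 8.1 and 8.2.1 on when film and PCV sampling stops. If followed, it leaves a child conscious from Day 2 without two earlier negatives with no scheduled film to meet the discharge rule. How many children this affects cannot be worked out from the documents. The printed total also omits the VENT blood-gas and HPS electrolyte samples without saying so. Nothing here touches the primary endpoint, sample size, power or type I error. The schedule conflict matters more than the missing 1 mL.

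**What to change.** - Confirm the admission volume, the fingerprick volume and the number of fingerpricks, and correct the total in Section 8.2.1. If the stated inputs stand, it is 4.6 mL.
- Reconcile the film and PCV rules in Sections 4, 8.1 and 8.2.1, the discharge criterion in Section 4 and the row in Appendix A to one schedule. Which schedule applies is for the sponsor to decide.
- Restate the blood total for the adopted schedule. If its length varies by child, give a range or a maximum.
- Either say that the total excludes VENT blood gases and HPS electrolytes, or add them by arm with stated sample volumes. The HPS figure must wait until the electrolyte frequencies in Sections 4, 6.3, 8.1 and 8.2.1 are reconciled.

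The cost is a text and table correction, plus the consent form if it repeats the figure, which cannot be seen here. No statistical analysis changes.

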8.3 Special Assays or Procedures

8.3.1 Fundoscopy

Fundoscopy will be performed at admission and every 24 hours (± 12 hours) thereafter until the patient reaches a BCS of 3 for greater than 4 hours. Pupils of participants will be dilated with mydriatics (a combination of 1.0% tropicamide hydrochloride and 2.5% phenylephrine hydrochloride) in both eyes. A trained clinician will perform direct and indirect ophthalmoscopy on fully dilated eyes. The elements of that will qualify a participant for being retinopathy positive in the study are presence one or more of the following:

- Retinal hemorrhages
- Whitening
- Vessel changes

Examples of each of these are included as Figure 3, Section 2.1g.

The presence or absence of papilledema will also be noted. Presence of papilledema alone without any of the other three elements will not qualify the participant for classification as retinopathy positive. The presence or absence of papilledema will however be evaluated as a measure of increased brain volume.

8.3.2 MRI

MRI of the brain will be the “gold standard” for assessing the presence of brain volume. The final determination of brain volume will be made initially by one of two experienced radiologists. They will use the following scale⁵²:

1 = severe atrophy markedly abnormal for age with diffuse prominence of the cisternae and sulci

2 = mild atrophy – subtle prominence of the cisternae and sulci for age

3 = normal brain volume

4 = mild increased volume but with maintenance of cisternae and sulci

5 = mild swelling – some loss of cisternae and sulci but not diffuse

6 = moderate swelling – diffuse involvement with some loss of cisternae and sulci

7 = severe swelling – loss of all sulci, presence of cisternal effacement, decreased gray/white matter delineation

[figure not shown]
8 = severe swelling – loss of all sulci, presence of cisternal effacement, presence of uncal herniation, loss of gray/white matter delineation

The presence of severely increased volume (edema score 7 or 8) identifies the subset of children who are most susceptible to herniation and therefore death (Figure 5). Real-time interpretations during the 2018 enrollment season revealed that neuroradiologists could not reliably differentiate a brain volume score of 6 or 7. In order to include all subjects who might benefit from the interventions, subjects with brain volume scores of 6-8 will be eligible for randomization (see Section 2.3.3).

Two study radiologists will be available at all times to review MRIs and assign a brain volume score. If both independently assigned brain volume scores are ≥ 6 , the participant will be eligible for randomization. If either independently assigned, real-time score is < 6 the participant will not be eligible for randomization.

Three other study radiologists will review all screening and study scans and will arrive at a consensus ‘brain volume score’ for each MRI scan on a regular basis and will complete the task within 1-month of the end of the enrollment period each year. If there is a discrepancy regarding the initial brain volume score and the consensus score in enrolled subjects any subjects incorrectly enrolled will be excluded from the ‘per protocol’ analyses but will remain in the ‘intention to treat’ analyses. If there is a discrepancy in the serial MRIs that affects the decision to withdraw the experimental treatment (VENT or HPS), the discrepancy will be noted; any subjects incorrectly withdrawn will be excluded from the ‘per protocol’ analyses, but will remain in the ‘intention to treat’ analyses.

8.3.3 Optic nerve sheath diameter (ONSD)

ONSD will be measured using a digital ultrasound machine with an appropriate transducer. Details of the ONSD determination procedure are as described in Tayal *et al*¹⁹⁶.

Figure 11 Illustration of the image and proper area for measurement in ONSD determination²⁵⁷.

8.3.4 Transcranial Doppler Ultrasound (TCD)

TCD will be measured using a commercially available TCD unit with an appropriate transducer. Details of the TCD examination are as described in Aaslid *et al*⁷². The following diagnostic criteria will be used to categorize studies into phenotypes:

Microvascular Obstruction

- 1) Systolic flow in middle cerebral arteries was within standard deviations (SD) of normal for age and gender AND
- 2) Diastolic flow in middle cerebral arteries was < 2 SD below normal for age and gender AND
- 3) Middle cerebral artery Gosling's pulsatility index was ≥ 1.2

Pulsatility Index (PI)= (Systolic flow velocity-Diastolic flow velocity/Mean flow velocity)

Hyperemia

- 1) Mean flow in middle cerebral arteries was ≥ 2 SD above the age and gender normal value AND
- 2) Ratio of flow between the middle cerebral artery and extra-cranial carotid artery (Lindegaard ratio (LR)) was < 3 AND
- 3) The dichrotic notch was absent on waveform morphology analysis of the middle cerebral artery AND

Cerebral Vasospasm

- 1) Mean flow in the middle cerebral arteries was ≥ 2 SD above age and gender normal value AND
- 2) LR was ≥ 3 AND
- 3) The dichrotic notch was present on waveform morphology analysis of the middle cerebral artery

Low Flow

- 1) Systolic, diastolic, and mean flows were equally reduced in the middle cerebral arteries $\leq 2SD$ below the age and gender normal value AND
- 2) The PI was < 1.2

Isolated Posterior Hyperemia

- 1) Mean flow velocity in the basilar artery was $\geq 2SD$ above age and gender normal value AND
- 2) Mean flow velocity in both middle cerebral arteries was within 2SD of age and gender normal value

Terminal Intracranial Hypertension

- 1) Systolic flow in the middle cerebral artery was $< 2SD$ below age and gender normal values WITH associated systolic spikes on waveform analysis AND
- 2) Absence of or reversal of diastolic flow was noted

